4.5.2. Exclusion Criteria

Subjects who meet any of the following exclusion criteria will be excluded from participation in this study:

- 1. Subjects with any serious medical condition or clinically significant laboratory, vital signs, or physical examination abnormality that would prevent study participation or place the subject at significant risk, as judged by the Investigator
- 2. Liver function tests excursions that exceed:
 - AST or ALT > 2X ULN
 - Total bilirubin:
 - > 1.5 x ULN or
 - > ULN and \leq 1.5 x ULN AND direct bilirubin is > 35% of total bilirubin
 - ALP $\geq 2x$ ULN
- 3. Subjects who cannot discontinue medications and treatments prior to the Baseline visit and during the study according to Excluded Medications and Treatments (Table).
- 4. Has unstable AD or any consistent requirement for high potency topical steroids to manage AD signs or symptoms.
- 5. Subjects who have significant active systemic or localized infection (e.g., molluscum contagiosum), including known actively infected AD, or have had any infection that required oral or intravenous administration of antibiotics, antifungal or antiviral agents within 14 days prior to Baseline/Day 1.

- 6. Subjects who are unwilling to refrain from prolonged sun exposure and from using a tanning bed or other artificial light emitting devices (LEDs) for 4 weeks prior to Baseline/Day 1 and during the study.
- 7. Subjects with skin conditions other than AD that would interfere with evaluations of the effect of the study medication on AD, as determined by the Investigator. Subjects with any condition on the treatment area which, in the opinion of the Investigator, could confound efficacy measurements, e.g., molluscum contagiosum.
- 8. Subjects with known genetic dermatological conditions that overlap with AD, such as Netherton syndrome.

Q	Known	allergies to	evcinients	in ARC	1.151	cream
フ.	MIIOMII	aneigies to	excipients	MAN(7-131	Cicaiii

- 10. Subjects who cannot discontinue the use of strong cytochrome P-450 CYP3A4 inhibitors e.g., indinavir, nelfinavir, ritonavir, clarithromycin, itraconazole, ketoconazole, nefazodone, saquinavir, suboxone and telithromycin for 2 weeks prior to the Baseline/Day 1 and during the study period.

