5.9. Treatment Stopping Rules

If a subject has non-cutaneous adverse events of concern, clinically significant laboratory values or any condition that the investigator determines could possibly be related to the study drug, the Investigator should immediately contact the Medical Monitor to discuss if the subject should be discontinued from treatment with investigational product.

Treatment for any individual subject will be discontinued if the subject experiences:

- A serious adverse event (SAE) or a clinically significant non-serious AE which in the opinion of the Principal Investigator or Medical Monitor warrants discontinuation from the study for that subject's well-being.
- A treatment-emergent severe (Grade 3) laboratory abnormality (confirmed by repeat sample; see Appendix 13 for more infomation).

A subject with a PHQ-8 or modified PHQ-A score ≥15 should receive immediate referral to a mental health professional, and Investigators in consultation with the mental health professional should consider interruption or discontinuation of the study drug

• Subjects with a PHQ-8 or modified PHQ-A score of 10-14 should be referred to a mental health professional for evaluation, regardless of the reason for their change in score

Subjects with a CDI-2 raw total score of \geq 32 should be referred to a mental health professional, and Investigators in consultation with the mental health professional should consider interruption or discontinuation of the study drug

• Subjects with a CDI-2 raw score of \geq 21 for females and \geq 22 for males should be referred to a mental health professional for evaluation

A subject that is experiencing suicidal ideation and behavior should be referred immediately to a qualified mental health care provider and consideration given to discontinuation from study drug.

As noted above, study treatment must be discontinued immediately in the event of a female subject's pregnancy.

Treatment should be interrupted:

• If a subject develops an application site reaction with the clinical appearance of an 'irritation reaction', and with a severity of a Dermal Response Score of 5 (erythema, edema and papules) or greater on the scale of Berger and Bowman, treatment should be interrupted for up to one week and may then be resumed if the reaction has, in the opinion of the Investigator, adequately resolved.

Treatment should be discontinued:

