6.6. Safety Analysis

Descriptive statistics will be calculated for quantitative safety data and frequency counts will be compiled for classification of qualitative safety data. The safety population will be used for these analyses.

Adverse Events:

The subject incidence of treatment-emergent adverse events (TEAE) will be summarized overall, by severity, and by attribution.

Clinical Laboratory Results:

Shifts in clinical laboratory parameters from baseline to worst post-baseline grade will be provided.

Vital Signs:

The subject incidence of >5% weight loss or gain on study will be provided, as well as whether weight loss was explained or unexplained.

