6.12. Clinical Laboratory Results and Vital Signs

All clinical laboratory results and vital signs measurements and their change from baseline (pre-dose), will be summarized descriptively by parameter, visit, and treatment group along with time point of collection.

A shift table describing out-of-normal range shifts will be provided for clinical laboratory results.

A shift table will identify subjects who gain or lose >5% body weight over the course of the study.

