1 INTRODUCTION

This Statistical Analysis Plan (SAP) describes the planned analysis and reporting for Arcutis Biotherapeutics, Inc. clinical protocol ARQ-151-311. The analyses described in the SAP are based upon the protocol Amendment 4 dated 28 September 2022. In case of changes (note that any such changes are described in section 3.5 below) between the protocol and the SAP, the SAP will be used to guide the statistical analysis. Any deviations from the SAP will be described and justified in the final Clinical Study Report (CSR), as appropriate.

On [REDACTED] FDA provided the following advice in preliminary feedback prior to a pre-NDA meeting held with Arcutis for a similar program on [REDACTED]

For the primary estimand, you [Arcutis] proposed a treatment policy strategy to handle all intercurrent events, including treatment discontinuation due to adverse event or lack of efficacy. For intercurrent events of treatment discontinuation due to adverse events or lack of efficacy, we [FDA] recommend a composite strategy policy where subjects will be defined as non-responders, as we consider this to be the appropriate approach for handling such events. Your proposal to handle intercurrent events of treatment discontinuation using the treatment policy strategy can be used as part of a supportive estimand.

The purpose of this version of the SAP is to document the change to the primary estimand and related multiple imputation strategies as requested by the FDA for a similar program.

This SAP has been developed prior to database lock, unblinding, and associated analyses. All final analyses will be performed after approval of the SAP, the clinical trial data are entered into the database, any discrepancies in the data are resolved, determination of the inclusion/exclusion of each subject from each analysis population, the database is locked, and the unblinding request form is signed.

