5.4 Windowing Conventions

Visits will be analysed as scheduled. Unscheduled, early termination visits, and/or retest measurements will only be included if a scheduled measurement is not available and the early termination or unscheduled/retest measurement falls within the analysis visit windows as described in [Table 2](#), [Table 3](#), and [Table 4](#) when appropriate. Unscheduled/retest measurements will be listed.

If there is more than one assessment for a given timepoint and analysis visit when a scheduled measurement is not available, the assessment closest to the target day will be considered.

	STATISTICAL ANALYSIS PLAN, Version 3.0
Protocol Number: ARQ-151-311	Sponsor: Arcutis Biotherapeutics, Inc.

Table 2 Analysis Visit Windows for Efficacy Endpoints, Vital Signs, CDI-2, PHQ-8, PHQ-A, C-SSRS and Local Tolerability Assessment

Analysis Visit	Target Day	Lower Limit	Upper Limit
Week 1	8	2	11
Week 2	15	12	22
Week 4	29	23	43

Table 3 Analysis Visit Windows for Clinical Laboratory, Physical Examination and PK assessment

Analysis Visit	Target Day	Lower Limit	Upper Limit
Week 4	29	23	43

Table 4 Windows for the derivation of Average Weekly WI-NRS

Days for calculation of weekly average	Week (Derived)
(-7, -1)*	Baseline
(1, 7)*	Week 1
(8, 14)	Week 2
(15, 21)	Week 3
(22, 28)	Week 4

* Day 1 WI-NRS score will be used to calculate the value for week 1 only when it is collected after the application of the first study drug (randomization for randomized subjects who were never treated with study drug). If Day 1 WI-NRS score is collected prior to or concurrently with the application of the first study drug (randomization for randomized subjects who were never treated with study drug), then the Day 1 WI-NRS score will be included in baseline calculation.

Note: With the caveat described in footnote **, if more than one WI-NRS score is available on the same day, the worst score of the day will be considered in the analyses.

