5.8 Handling of Retests, Unscheduled Visits, and Early Termination Data

Retests measurements, Unscheduled measurements, and ET visit assessments will be included in analysis and be summarized via analysis visit windowing according to the windowing conventions in section 5.4.

All data from retest, unscheduled measurements and ET visit assessments will be listed.

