13.2 Clinical Laboratory

Descriptive statistics for the observed values in chemistry, hematology, and quantitative urinalysis, change from baseline and percent change from baseline values will be presented by treatment group at each scheduled visit. For qualitative urinalysis data, the number and percentage of the subjects for each level of result by treatment at each scheduled visit will be provided.

Shift tables from baseline to each postbaseline assessments describing shifts to out-of-normal range will be provided for chemistry, hematology, and qualitative urinalysis. Only subjects with a baseline result and a result at the specified visit for the parameter will be considered.

Listings of abnormal laboratory will be provided for each parameter where a subject had at least one abnormal result.

Laboratory data will be presented in SI units.

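### SAP 13.2 plans no by-arm table of toxicity grade or worst post-baseline value for chemistry and hematology, and post-baseline off-schedule results enter a summary only under a narrow rule (minor)

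*SAP*

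**What the plan says.** SAP 13.2 plans four laboratory outputs:

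- descriptive statistics by scheduled visit;
- counts per result level for qualitative urinalysis, by scheduled visit;
- range-based shifts: "Shift tables from baseline to each postbaseline assessments describing shifts to out-of-normal range will be provided for chemistry, hematology, and qualitative urinalysis";
- listings of abnormal results.

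The sentence after the shift table limits it to subjects with a baseline result and a result at the visit in question.

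Off-schedule data follow SAP 5.4: "Unscheduled, early termination visits, and/or retest measurements will only be included if a scheduled measurement is not available", with the further condition that the value lies inside the analysis window. SAP Table 3 gives laboratory data one post-baseline window, Week 4, Days 23 to 43. SAP 5.8 uses the same route: "Retests measurements, Unscheduled measurements, and ET visit assessments will be included in analysis and be summarized via analysis visit windowing". It adds that all such data are listed.

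The supplied protocol plans two shift tables. Section 6.12 has the range-based one: "A shift table describing out-of-normal range shifts will be provided for clinical laboratory results". Sections 6.6 and 6.8 also plan a graded one: "Shifts in clinical laboratory parameters from baseline to worst post-baseline grade will be provided". Section 5.9 makes the following a reason to discontinue treatment: "A treatment-emergent severe (Grade 3) laboratory abnormality (confirmed by repeat sample", with cut-offs in Appendix 13. Exclusion 2 sets the entry limit for the transaminases: "AST or ALT > 2X ULN".

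The supplied protocol is the original. The SAP says its analyses are "based upon the protocol Amendment 4 dated 28 September 2022", and that version is not among the documents.

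**The concern.** The main use of laboratory tables in a descriptive safety analysis is to show how many subjects in each arm had a marked abnormality at any time on treatment. A range-based shift by visit does not do this. It merges every excursion above the limit into one category, and it shows only the result assigned to the visit.

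The windowing rule adds to the problem. Off-schedule samples are often taken because something looks abnormal, and the Grade 3 rule in Protocol 5.9 itself calls for a repeat sample. Those are the results most likely to reach a listing and no summary. The trial could then finish without a planned by-arm count of how often a Grade 3 chemistry or hematology value occurred, or was confirmed. The stake is the completeness of safety reporting. Efficacy and type I error are not involved.

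**Working it through.** The plan states no figure on this point, so there is none to reproduce. The check applies the stated rules to the stated cut-offs.

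**Step 1. Range against grade.** Inputs: Exclusion 2 (entry allowed up to 2xULN for ALT and AST) and Appendix 13.

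| ALT or AST | Appendix 13 | Range category |
|---|---|---|
| >ULN to 3xULN | Grade 1 | high |
| >3 to 5xULN | Grade 2 | high |
| >5xULN | Grade 3 | high |

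A subject at 2xULN at baseline is already high. Reaching Grade 3 takes a rise of more than 5 / 2 = 2.5-fold. The range-based table records this as high to high, which is no shift. On the Appendix 13 scale it is Grade 1 to Grade 3.

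**Step 2. Which post-baseline off-schedule results are summarised.** From SAP 5.4 and Table 3, a result is used only if no scheduled Week 4 result exists AND 23 ≤ day ≤ 43.

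| Example | No scheduled result? | Day 23 to 43? | Summarised? |
|---|---|---|---|
| Early-termination sample, Day 10 | yes | no | no |
| Unscheduled sample Day 15, scheduled sample Day 29 | no | no | no |
| Retest Day 31 after scheduled sample Day 29 | no | yes | no |
| Early-termination sample Day 25, no scheduled sample | yes | yes | yes |

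The rule bites only after baseline. SAP 5.2 allows a pre-dose unscheduled or retest value to serve as baseline, and such a value then enters the change and shift tables.

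**Step 3. Extent in time.** Days 2 to 22 are 21 days. Days 2 to 28 are 27 days. 21 / 27 = 78% of the on-treatment days after Day 1 lie outside the only post-baseline laboratory window. No laboratory draw is scheduled on those days, so this is a share of calendar days. It does not measure lost results.

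**Step 4. What the other planned outputs show.**

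- *Minima and maxima (SAP 5.6, applied in 13.2).* An extreme Week 4 value would move the arm's maximum. This gives one value per arm, with no count of subjects.
- *Qualitative urinalysis by level (13.2).* Appendix 13 sets Grade 3 for dipstick protein and glucose at above 2+. If results are reported by dipstick level, this table could give Week 4 Grade 3 counts by arm. It does not cover chemistry or hematology.
- *TEAEs by maximum severity and leading to discontinuation (13.1).* These count by arm, but only findings recorded as adverse events. Protocol 5.7.1 generally leaves out abnormal results judged not clinically significant.
- *Listings.* These are complete for off-schedule values but give no rate.

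None of the four gives a by-arm count of subjects reaching Grade 3 in chemistry or hematology over the whole treatment period.

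**Step 5. Gradable entries.** Protocol Table 3 has 11 chemistry + 5 hematology = 16 entries. Appendix 13 has rows for 10 of the 11 (not chloride) and 3 of the 5 (not hematocrit or red-cell count), so 13. Four of these scale to ULN (ALT, AST, ALP, bilirubin). The other 13 − 4 = 9 have fixed Grade 3 cut-offs.

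**The case against.** The strongest reply is that serious laboratory events will not be lost. A confirmed Grade 3 value on treatment leads to discontinuation. A finding that requires a change of therapy is an adverse event under Protocol 5.7.1, and SAP 13.1 tabulates those events by arm. Range-based shifts with listings are also a defensible convention. The only scheduled post-baseline sample is at Week 4, when the 28-day course is normally complete, so a repeat taken then seldom bears on a stopping decision. Appendix 13 was written for healthy adults, which makes it an awkward scale for a trial with many children.

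Much of this stands, and it is why the point is minor. What remains are unconfirmed Grade 3 values, values judged not clinically significant, and off-schedule values that never became adverse events. It does not help to argue that adverse events are graded on a different scale: Appendix 13 labels its ALT, AST, ALP and bilirubin rows as CTCAE 4.0. The gap lies in which findings become adverse events.

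The loose phrase about each post-baseline assessment in SAP 13.2 might be read as covering off-schedule samples. The following sentence and SAP 5.8 tie the table to the windowed visit.

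A reader might also infer that the SAP silently dropped a protocol commitment, since SAP 3.5 lists no such change. The documents do not support that. The commitment is in the original protocol, the SAP follows Amendment 4, and whether Amendment 4 kept the graded shift table cannot be checked.

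**Conclusion.** The point holds for chemistry and hematology. SAP 13.2 has no grade or worst-value table, range-based shifts cannot separate Grade 1 from Grade 3, and post-baseline off-schedule results outside the two conditions of SAP 5.4 are only listed.

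Its size cannot be given in subjects or samples, because the number of off-schedule draws is unknown. The 78% in the working should not be read as a loss of data. It would also go too far to say that Grade 3 values would be invisible, or that no planned table could show any Grade 3 count; Step 4 shows the partial cover. Safety analysis is descriptive (SAP 13), so no inferential conclusion changes.

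The case assumes that the Grade 3 stopping rule and Appendix 13 survive in Amendment 4, which is unverified. If they were removed, the lack of any worst-value summary would remain, but the choice of scale would need a new justification. Severity: minor, a cheap improvement.

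**What to change.** Add to SAP 13.2, by arm:

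1. a shift from baseline grade to worst post-baseline grade, using Appendix 13;
2. the number and percentage of subjects with any treatment-emergent Grade 3 value, and with one confirmed by repeat.

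Use all post-baseline results, including unscheduled, retest and early-termination ones, regardless of the SAP 5.4 windows. Take as denominator the subjects with any post-baseline result for the parameter. This matters because children aged 6 to 11 who entered under Amendment 2 have no scheduled post-baseline sample (SAP Table 1, note b).

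Grade the four ULN-scaled parameters (ALT, AST, ALP, bilirubin) at all ages. Grade the nine fixed-cut-off parameters in adults, and in under-18s only where age-specific ranges or a pre-stated rule exist; Appendix 13, footnote a, allows for grading by age and sex. Leave parameters without a row ungraded. Keep the out-of-range table. If Amendment 4 still contains the graded shift table and its omission is deliberate, record that in SAP 3.5 with the reason.

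The cost is one extra table, the grade coding and a short paediatric grading rule. The data are already collected, and nothing changes in trial conduct, alpha or the efficacy analyses.

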13.3 Vital Signs

Descriptive statistics will be presented for vital signs (systolic blood pressure, diastolic blood pressure, heart rate, body temperature, and weight). Observed values, change from baseline and percent change from baseline values will be presented by treatment group at each scheduled visit.

The number and percentage of subjects with gain or lose $>5\%$ from baseline in body weight over the course of the study will be summarized for overall and separately for children and adolescents (6 to 17 years) and adults (≥ 18 years). BMI will be summarized using descriptive statistics (n, mean, standard deviation, median, Q1, Q3, minimum, and maximum) on observed values, change from baseline and percent change from baseline values separately for children and adolescents (6 to 17 years) and adults (≥ 18 years). The BMI percentile rather than BMI kg/m^2 will be summarized for children and adolescents (6 to 17 years).

A listing of all vital sign assessments including weight, BMI, and BMI percentile for children and adolescents will be provided.

	STATISTICAL ANALYSIS PLAN, Version 3.0
Protocol Number: ARQ-151-311	Sponsor: Arcutis Biotherapeutics, Inc.

13.4 Local Tolerability Assessments

The investigator's assessment of the application site reaction will be summarized by visit using both categorical methods (number and percentage of subject with each score) as well as continuous methods (e.g., mean, standard deviation, etc.)

Local tolerability (burning/stinging sensation) assessed by the subject will be summarized using number and percentage similarly.

13.5 Patient Health Questionnaire Depression Scale (PHQ-8) and Patient Health Questionnaire Depression Scale (Modified PHQ-A)

The Modified PHQ-A Assessment will be performed in adolescent subjects (12-17 years old, inclusive; question 9 has been removed since that is better evaluated by use of the C-SSRS tool).

The PHQ-8/Modified PHQ-A score is the sum of the responses for the questions, each question ranging from 0 (Not at all) to 3 – (Nearly every day). Five severity categories of depression are defined as follows:

- None – Minimal depression (0 to 4)
- Mild depression (5 to 9)
- Moderate depression (10 to 14)
- Moderately severe depression (15 to 19)
- Severe depression (20 to 24)

The score will be set to missing in case of at least one missing value. The number and percentage of subjects in each category will be summarized by treatment and visit. A summary of the shifts in depression category from baseline to each study visit will also be provided.

